## 6.7 Data Collection

Data management will be performed by the study personnel under the direction of the study PI. GU and GI toxicity data will be collected at all sites using an appropriate adverse events (AE) application, such as NCI's Cancer Adverse Event Reporting System (caAERS). Demographic, pathology, PSA, IIEF, AUA and other pertinent study data will

be collected at all sites and entered into a study specific secure database. See Appendix 3 for data fields.

#### 6.8 Adverse Events Classification

Adverse events will be recorded at each study visit. These adverse events will be classified in accordance to the CTCAE ver. 4.0.

#### 7.0 Statistical Analysis Plan

#### 7.1 Primary End Point

The primary end-point of the study is the safety of delivering SBRT to the prostate. The dose and fractionation of radiation is determined such that the risk of late complications should be equivalent to the  $BED_{3Gy}$  of 78 Gy in 2 Gy fractions.

A conservative estimate of grade 3 rectal toxicity for this regimen of 78 Gy in 2 Gy fractions is 1.5% at 2 years. Therefore, with a patient population of 60 patients if the true rate of grade 3 or higher rectal toxicity is 1.5% there will be a 77% power to rule out a >7.1% rate. If the true rate is 2.5%, there will be an 81% power of ruling out a >9.6% rate.

#### Incidence of GU and GI Acute and Late Adverse Events

Adverse events are scored according to CTCAE version 4.0. An acute adverse event will be defined as an adverse event occurring less than or equal to 90 days from the completion of RT. Both unadjusted and adjusted odds ratios and the respective 95% confidence interval will be computed.

A late adverse event will be defined as an adverse event occurring more than 90 days from the completion of RT. The time to late adverse events will be measured from the time that protocol treatment is completed (i.e., the completion of radiation) to the time of the worst late adverse event. If no such late adverse event is observed until the time of the analysis, the patient will be censored at the time of the analysis. The distribution of time to late adverse events (observed severities of adverse events over time) will be estimated.

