# 2.0 Objectives

# 2.1 Primary Objective

To evaluate the incidence of GU and GI acute and late toxicity (see Section 8.1) for patients treated with prostate stereotactic body radiotherapy (SBRT) along with prostate

localization (Calypso or ExacTrac and onboard cone-beam CT) and IMRT reoptimization for each fraction based on the anatomy of the day.

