# 3.0 Study Design and Patient Selection

# 3.1 Study Design

This is a Phase II single institution investigator-initiated trial where the primary end-point is the assessment of Grade 2+ late toxicity 2 years from the start of treatment. Based upon an assumed linear rate of grade 2 or greater toxicity from 18-36 months after the completion of treatment the primary end-point will be assessed when all patients have completed treatment, have a minimum of 3 months of follow-up, and a cumulative 120 person/years of follow-up have been recorded (an average of 2 years per patient).

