**Dose Fractionation** 

Patients will receive 5 fractions of radiation. Each fraction size will be 7.4 Gy. The total dose will be 37 Gy. The 5 treatments will be scheduled to be delivered every other day. A minimum of 36 hours should separate each treatment. No more than 3 fractions will be delivered per week. The total duration of treatment will be no shorter than 10 days and no longer than 18 days.

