# 7.3 Sample Size and Patient Accrual

We anticipate that this study will begin enrolling subjects in the Fall 2009 and will enroll 2 subjects a month for 30 months for a total enrollment of 60. This projection is based on the 250 newly diagnosed prostate cancer patients seen in the Department of Radiation Oncology each year, of which at least 75 should be eligible for this study.

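### Acute GU and GI toxicity is part of the primary objective, but its only stated analysis is odds ratios with no named contrast, which do not estimate incidence

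*Combined protocol and SAP*

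**What the plan says.** Section 2.1 states the primary objective: "To evaluate the incidence of GU and GI acute and late toxicity". Section 3.1 is narrower: "This is a Phase II single institution investigator-initiated trial where the primary end-point is the assessment of Grade 2+ late toxicity 2 years", counted from when treatment begins.

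There is one treatment group. The Schema shows a single arm, and the Dose Fractionation text in Section 5.1 applies to everyone: "Patients will receive 5 fractions of radiation. Each fraction size will be 7.4 Gy". Section 7.3 sets the size: the study "will enroll 2 subjects a month for 30 months for a total enrollment of 60".

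The analysis is in Section 7.1, under a sub-heading about the incidence of acute and late adverse events. It first sets the window: "An acute adverse event will be defined as an adverse event occurring less than or equal to 90 days from the completion of RT". The next sentence is the only analysis that follows this definition: "Both unadjusted and adjusted odds ratios and the respective 95% confidence interval will be computed". It gives no factor, comparison group, model, covariate or grade threshold. The text then turns to late events, which have their own time-to-event analysis: "The distribution of time to late adverse events (observed severities of adverse events over time) will be estimated".

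**The concern.** An incidence in one treated cohort is a proportion: men with an event over men treated. An odds ratio compares the odds of an event between two groups or across levels of a factor. The plan names nothing to compare, so the quantity is undefined as written. Supplying a factor later would make it computable, but it would then answer a question about association.

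If the plan is followed literally, the acute component of the objective has no prespecified estimate and no stated precision. The grade that counts as an event, the denominator and the interval method could all be settled after the data are seen. So could the factor and the covariates for the odds ratios.

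**Working it through.** **1. The plan's own figures.** No figure is stated for acute toxicity. The nearest are the two power statements in Section 7.1 for grade 3+ rectal toxicity with n = 60.

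- True rate 1.5%: P(X ≤ 1) = 0.4038 + 0.3690 = 0.7728, the stated 77%.
- True rate 2.5%: P(X ≤ 2) = 0.2189 + 0.3368 + 0.2548 = 0.8105, the stated 81%.
- The Wilson one-sided 95% upper limits for 1/60 and 2/60 are 7.13% and 9.58%, the stated 7.1% and 9.6%.

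Both statements reproduce, and both treat toxicity as a single-arm proportion. The odds-ratio sentence departs from that framework.

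**2. Can an odds ratio supply the incidence?** Take two equal subgroups with reference rate p0 and odds ratio 2. Then p1 = 2o/(1 + 2o), where o = p0/(1 − p0), and the overall incidence is (p0 + p1)/2.

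| p0 | p1 | Overall incidence |
|---|---|---|
| 5% | 9.5% | 7.3% |
| 20% | 33.3% | 26.7% |
| 40% | 57.1% | 48.6% |

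The same odds ratio is compatible with very different incidences, so it does not determine the target quantity.

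**3. How precise would a within-cohort odds ratio be?** Assume a 30/30 split and a true odds ratio of 1, with a events and b non-events per subgroup. The standard error of the log odds ratio is √(2/a + 2/b), and the 95% interval is exp(±1.96 × SE).

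- 6 events (a = 3, b = 27): SE = √(0.667 + 0.074) = 0.861; interval about 0.19 to 5.4.
- 12 events (a = 6, b = 24): SE = √(0.333 + 0.083) = 0.645; interval about 0.28 to 3.5.

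**4. What would a proportion give?** The exact (Clopper-Pearson) two-sided 95% limits are the 2.5% quantile of Beta(x, n − x + 1) and the 97.5% quantile of Beta(x + 1, n − x), with n = 60. The counts are assumed.

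| Men with event | Proportion | Exact 95% interval |
|---|---|---|
| 3 | 5% | 1.0% to 13.9% |
| 12 | 20% | 10.8% to 32.3% |
| 30 | 50% | 36.8% to 63.2% |

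The half-width is largest at 50%: (63.2 − 36.8)/2 = 13.2 points.

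**5. Does another section fill the gap?**

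- The power statement in Section 7.1 concerns grade 3+ rectal toxicity, with its reference rate given at 2 years. It covers neither GU nor grade 2 events.
- The late-event analysis in Section 7.1 starts beyond 90 days.
- Section 7.4 sets 5% as acceptable and 20% as unacceptable for grade 3+ GU and GI events over 24 months from the start of radiation. That window contains the acute period, but the rule pools acute with late events, omits grade 2 and serves to stop or continue accrual.

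None of these plans an acute proportion or an interval for one.

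**The case against.** The strongest defence is that the sub-heading and Section 2.1 both speak of incidence. On that reading proportions will be reported as a matter of course, and the odds ratios are an under-specified addition. The sentence does not contain the word acute and is tied to acute events only by its position. The intent is plausible, and the documents do not say that proportions will be withheld. But no proportion, grade threshold, denominator or interval is written down. If the sentence is taken as not referring to acute events, they have no stated analysis at all.

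A reader might infer that odds ratios are meaningless in a one-arm trial. The documents do not support that. Appendix 3 collects localization mode (Calypso or ExacTrac), rectal and bladder dose-volume data and baseline AUA score, any of which could define a contrast. What stands is that none is named, and that the result would not be an incidence.

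A reader might also infer that half of the primary objective goes unanalysed. That is too strong. Section 3.1 makes late grade 2+ toxicity the end-point, and the power statement does not depend on acute events. The gap concerns one component of the objective.

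Finally, the 20% grade 2 GU rate (8/40) of the first series in Section 1.3 might be taken as an expected acute rate. It follows a definition of late toxicity as 30 or more days after therapy and a statement at 41 months' median follow-up, so it reads as a late rate. It gives no basis for an acute forecast here.

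**Conclusion.** The acute analysis is wrong as written: the stated statistic has no defined contrast, and no choice of factor would turn it into an estimate of incidence. This is more than a missing detail, because filling in the detail would still leave the question unanswered. It should be corrected before analysis, but it does not affect the sample size, the power statement or the late end-point.

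The conclusion does not depend on any event rate. The precision figures do: they assume the counts shown and that all 60 men are treated and assessed. The odds-ratio intervals also assume an even split and no true association. At worst the study would estimate an acute proportion to within about 13 points either way, which is useful for a descriptive result.

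**What to change.** Replace the odds-ratio sentence in Section 7.1 with:

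*For acute GU and acute GI toxicity separately, the number and proportion of treated men whose worst grade is 2+ and 3+ will be reported with exact two-sided 95% confidence intervals, each man counted once.*

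Delete the odds ratios, or keep them as explicitly exploratory for one baseline or technical factor named in advance, with the model stated. The two thresholds and the exact method are one reasonable choice. What matters is that a threshold, a denominator and an interval method are fixed beforehand.

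The cost is wording only. Section 6.6 already schedules toxicity assessment during radiotherapy and at 1 and 3 months, and Section 6.8 already grades events by CTCAE version 4.0, so no extra patients, visits or data items are needed.

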# 6.5 Follow-up Visits

Patients will be seen approximately at 1, 3, 6, 12, 18, 24, 36 months following the end of radiotherapy. Follow-up visits may occur at the Department of Radiation Oncology or with referring providers. At each visit (see table) the patient will have an interval history, focused physical examination (digital rectal examination at the physician discretion), and assessment of specific GU and GI toxicity. PSA will be assessed before or at each follow-up visit.

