## 6.6 Patient Assessments

Patient assessments are described below, some variation with respect to visit timing is permissible to allow for individual patient needs and clinic schedules.

	Baseline	SBRT Planning	During RT	1 Mo	3 Mo	6 Mo	12 Mo	18 Mo	24 Mo	36 Mo
Medical History	Х									
Physical Exam	X (including DRE)			$\mathbf{X}^1$						
Planning CT/MR		Х	$X^2$							
Prostate Measurement	Х									
Transponder or Fiducial Marker Placement		Х								
AUASS, IIEF	Х			Х	Х	Х	Х	Х	Х	Х
EPIC-26 QOL	Х				Х		Х		Х	Х
Toxicity Assessment			X	X	X	X	X	X	X	X
PSA	$X^4$				Х	Χ	Х	Χ	Χ	Х

Focused physical exam. Digital rectal exam (DRE) at the discretion of the physician.

 CBCT to be performed prior to each treatment and reoptimization performed if needed.

 As per standard clinic practice.

 Baseline PSA must be within 180 days of study registration.

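### The planned late-toxicity analysis does not estimate the stated 2-year endpoint, and its censoring date biases the rate low if men are lost or events are dated at onset

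*Combined protocol and SAP*

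**What the plan says.** Section 3.1 states that "the primary end-point is the assessment of Grade 2+ late toxicity 2 years from the start of treatment". The analysis takes place once all men have finished treatment, "have a minimum of 3 months of follow-up, and a cumulative 120 person/years of follow-up have been recorded".

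Section 7.1, under Incidence of GU and GI Acute and Late Adverse Events, starts the clock at the end of radiotherapy and runs it "to the time of the worst late adverse event", with no grade threshold. For a man with no late event, "the patient will be censored at the time of the analysis". The text says the distribution will be estimated but names no estimator.

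On timing, Dose Fractionation (Section 5.1) says "The total duration of treatment will be no shorter than 10 days and no longer than 18 days", and Section 6.5 says "Patients will be seen approximately at 1, 3, 6, 12, 18, 24, 36 months following the end of radiotherapy". Section 6.6 adds that "some variation with respect to visit timing is permissible to allow for individual patient needs and clinic schedules". Section 6.8 has adverse events recorded at study visits. For events more than 30 days after treatment, Section 5.9 sets reporting times only for certain related serious events. Nothing says how a grade 2 event between visits would be found, whether an event is dated at onset or at the visit that finds it, or how men lost to follow-up are handled.

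**The concern.** Late toxicity is the primary endpoint, so the event, the origin and the censoring rule together define the result. Here they do not match the endpoint: worst event instead of reaching grade 2+, and end of treatment instead of start.

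The censoring rule adds a possible bias. A lost man stays in the risk set until the analysis date with no chance of a recorded event. If events are dated at onset, the time since each man's last visit also counts as event-free although nobody has assessed it. Both effects lower the estimated rate, which is the reassuring direction for a safety endpoint. Two analysts following this plan could report different 2-year rates from the same data.

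**Working it through.** **1. The plan's own figures.** For 60 men and a true rate of 1.5%, P(X ≤ 1) = 0.985^60 + 60 × 0.015 × 0.985^59 = 0.773. At 2.5%, P(X ≤ 2) = 0.810. One-sided 95% Wilson upper limits are 7.13% for 1/60 and 9.58% for 2/60. The 77% and 81% in Section 7.1 therefore reproduce. They are binomial statements on grade 3+ rectal toxicity and do not depend on the censoring rule. The Section 7.4 rules use counts and are also unaffected.

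**2. Endpoint against analysis.**

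| | Section 3.1 | Section 7.1 |
|---|---|---|
| Event | grade 2+ late toxicity | worst late event, any grade |
| Origin | start of treatment | end of radiotherapy |
| Time point | 2 years | none given |

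**3. Loss with visit-dated events, by hand.** Assumptions: true 24-month rate 26% (the grade 2+ rectal rate that Section 1.1 quotes for 78 Gy, used only as illustration); onset linear from month 3; exponential loss of a fraction L over 36 months, unrelated to toxicity; events found at the next attended visit. Keeping lost men in the risk set estimates the chance of a *recorded* event:

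26% × [3(1−L)^(6/36) + 6(1−L)^(12/36) + 6(1−L)^(18/36) + 6(1−L)^(24/36)] / 21

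- L = 10%: 26% × (2.948 + 17.078)/21 = 26% × 0.954 = 24.8%.
- L = 20%: 26% × (2.890 + 16.107)/21 = 26% × 0.905 = 23.5%.

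The relative deficit, about 5% and 10%, is the same at other true rates: 12% reads 11.4% and 10.9%.

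**4. Simulation.** Same assumptions, accrual of two men a month for 30 months, 4,000 trials of 60 men, Kaplan-Meier at 24 months from the end of treatment. Mean estimates (%), analysis-date censoring / last-assessment censoring:

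| Analysis month | Loss | Visit-dated | Onset-dated |
|---|---|---|---|
| 39 | 0 | 25.8 / 25.8 | 23.4 / 25.8 |
| 39 | 10% | 24.8 / 26.0 | 22.5 / 26.0 |
| 39 | 20% | 23.3 / 25.8 | 21.2 / 25.8 |
| 43.5 | 0 | 26.0 / 26.0 | 24.7 / 26.0 |
| 43.5 | 10% | 25.0 / 26.2 | 23.8 / 26.2 |
| 43.5 | 20% | 23.5 / 26.0 | 22.4 / 26.0 |

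The onset-dated columns assume nothing is reported between visits, so they are an upper bound on that bias. A second simulation, with constant hazard and loss counted by month 24, agrees: a true 20% reads 18.5% (10% loss, visit-dated) and 18.3% (no loss, onset-dated).

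**5. Time origin.** Radiotherapy lasts 10–18 days, or 0.33–0.59 months. With onset dating, reading at 24 months from the start costs 26/21 × 0.33 to 0.59 = 0.4 to 0.7 points. With visit dating and visits exactly on schedule, the cut-off falls before the 24-month visit and drops the events found there: 26% × 15/21 = 18.6%. With visits within an assumed ±1 month it gives 20.3–20.5%.

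**6. The 120 person-years.** Take two entries a month at mid-month, with follow-up counted from entry. At month 39, potential follow-up is 60 × (39 − 15)/12 = 120.0 person-years. Follow-up to the last scheduled visit is (6×6 + 12×12 + 12×18 + 24×24 + 6×36)/12 = 1,188/12 = 99.0, and 30 of 60 men have under 24 months. At month 43.5, follow-up to the last visit is (8×12 + 12×18 + 24×24 + 16×36)/12 = 1,464/12 = 122.0. The trigger therefore moves by about 4.5 months depending on which is meant.

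**7. Worst-event timing.** With 10–50% of events worsening later, one model gives 0.1 to 1.8 points too low. Another, with 30% worsening within 18 months, gives 0.2 to 0.5 points too high. The direction is not settled.

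**The case against.** - **The bias is conditional.** The documents give no loss rate, and recording at visits (Section 6.8) fits visit dating at least as well as onset dating. With visit dating and no loss the bias is nil. This stands.
- **It is small.** A shift of about 1 point at 10% loss compares with a sampling SD of about 7 points, and no power figure or stopping rule moves. This also stands.
- **The estimator is assumed.** Section 7.1 does not name Kaplan-Meier or a 24-month reading. That is correct; a person-time rate would move in the same direction, but its size was not computed.
- **The usual remedy can be worse.** With visits ±1 month, actual visit dates, no loss and a reading at month 25, last-assessment censoring gives 34.9% (month 39) and 31.2% (month 43.5), because men leave the risk set at their own visit. The current rule gives 25.7% and 26.2% in that setting. This limits which fix is acceptable; it does not rescue the current rule when men are lost.
- **The 18.6% case is extreme.** It needs visits exactly on schedule, and Sections 6.5 and 6.6 allow variation.
- **Section 3.1 speaks of follow-up that has been recorded**, which favours observed over potential time. That is the more natural reading, but it is not stated.

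None of these points removes the mismatch between Sections 3.1 and 7.1, which needs no assumption.

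**Conclusion.** The concern holds. On the text alone, the Section 7.1 analysis differs from the Section 3.1 endpoint in event, grade threshold and origin. The censoring bias is real but conditional. At an assumed true 26% it is about 1 point at 10% loss and 2.5 points at 20% with visit dating, and 1.3 to 2.4 points with onset dating and no loss. It is nil with visit dating and no loss. These sizes rest on assumed loss unrelated to toxicity, linear onset and a Kaplan-Meier reading at 24 months. No bias claim should rest on worst-event timing. This should be fixed because the reported 2-year rate depends on choices the plan makes wrongly or leaves open. It does not undermine the design.

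**What to change.** Amend Sections 3.1 and 7.1 so that they agree:

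- Define the analysis as time to the **first** late grade 2+ GU/GI event from one stated origin. Keep worst grade as a descriptive table.
- Pair event dating with censoring: either onset date with censoring at the last toxicity assessment, or scheduled visit month for both. Both pairings gave 25.8–26.2% in all 12 settings with loss unrelated to toxicity. Do not combine actual visit dates with last-assessment censoring.
- If events are visit-dated, the 2-year reading must include the 24-month visit.
- Treat death as a competing event. Report the 24-month cumulative incidence with 95% CI and numbers at risk.
- State whether the 120 person-years count time to last assessment or potential follow-up.
- Add a sensitivity analysis for loss related to toxicity.

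The cost is SAP wording, with no added patients or visits. The interval widens slightly: at month 39 the SD is 7.3 against 7.0 points at 10% loss, and 7.4 against 6.6 at 20%. If person-years run to the last assessment, the analysis falls at about month 43.5 without loss, 44.5 at 10% loss and 46.5 at 20%, instead of month 39.

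The new rule still assumes that loss is unrelated to toxicity. At 20% loss, if event-prone men are lost at three times the rate, it gives 24.2–24.3% (current rule 21.9–22.0%). If they are lost at one third the rate, it gives 27.4–27.8% (current rule 24.7–25.0%), overshooting by about as much as the current rule undershoots. Hence the sensitivity analysis.

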## 7.2 Secondary End-Points

- 7.2.1 Disease-free survival: Disease-free failure events include local progression, distant progression, biochemical recurrence as defined by the RTOG Phoenix definition, and death from any cause.
- 7.2.2 Analysis for Endpoints Related to EPIC-26 QOL

We will use the Expanded Prostate Cancer Index Composite (EPIC-26) instrument to measure QOL. Protocol eligible patients will be included in the QOL analysis only if they have provided baseline and at least one subsequent measurement. The EPIC-26 instrument is intended to be collected on all cases participating in the trial.

The EPIC-26 will be collected at pretreatment (baseline) and at 3, 12, 24 months, and 3 years after therapy starts. Patient self-assessment of symptoms will be performed using three primary EPIC scales: urinary, bowel, and sexual symptoms.

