## A Phase II Study of Stereotactic Body Radiotherapy (SBRT) for Prostate Cancer Using Continuous Real-time Evaluation of Prostate Motion and IMRT Plan Reoptimization based on Same Day Anatomy

**Principal Investigators** 

Radiation Oncology W. [name], MS, M. Ed. Department of Radiation Oncology Duke University [name] [contact] [contact] [contact]

Physics Q. [name]. Department of Radiation Oncology Duke University [name] [contact] [contact] [contact]

Version Date: June 17, 2013

NCT00941915

S	CHEMA	
Gleason Score		Treatment Arm
1. ≤6		
2. 7	dy	
PSA	Stu	7.4 Gy for 5 fractions
1. $\leq$ 15 ng/mL if Gleason $\leq$ 6	ц	delivered every other day;
2. $\leq 10 \text{ ng/mL}$ if Gleason 7	L O	IMRT/IGRT with
	ite	reoptimization for each
	.50	fraction
T stage	Se	
T1-2		

Treatment is prescribed as a minimum to the planning target volume (PTV) to be delivered at a daily dose of 7.4 Gy/ fraction. The PTV includes with CTV (prostate only) with a nonuniform margin.

Patient Population: (See Section 3.0 for Eligibility)

- Histologically confirmed prostate adenocarcinoma within 365 days prior to registration
- Clinical stage T1-2 according to the AJCC 6th edition
- Pretreatment PSA ≤10 ng/mL if Gleason 7 or ≤ 15 ng/ml if Gleason ≤6 (within 180 days of registration)
- Gleason score must be  $\leq 7$
- No previous radical surgery or cryosurgery for prostate cancer
- No prior or planned androgen deprivation or bilateral orchiectomy

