# 2.2 Secondary Objectives

- 2.2.1 Disease-free survival: Disease-free failure events include local progression, distant progression, biochemical failure as defined by the RTOG Phoenix definition, and death from any cause.
- 2.2.2 Evaluate patient quality of life (QOL) using the Expanded Prostate Cancer Index Composite 26 (EPIC-26) for evaluation of the QOL for up to 3 years after the completion of SBRT.

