# 2.3 Duration of Investigation and Expected Enrollment Rate

Men will be enrolled on study after meeting eligibility criteria and signing consent. Followup will continue for each enrollee up to three years after enrollment. It is estimated that a subject will be involved in the study for 36 months. We anticipate that this study will begin enrolling subjects in the Fall 2009 and will enroll 2 subjects a month for 30 months for a total enrollment of 60.

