# **3.3** Exclusion Criteria

3.3.1 Prior or concurrent invasive malignancy (except non-melanomatous skin cancer) or lymphomatous/hematogenous malignancy unless continually disease free for a

minimum of 5 years. (For example, carcinoma in situ of the bladder or oral cavity is permissible)

- 3.3.2 Evidence of distant metastases (based on disease stage and clinical presentation)
- 3.3.3 Evidence of regional lymph node involvement (based on disease stage and clinical presentation)
- 3.3.4 Significant urinary obstruction (i.e. AUA Symptom score > 18)
- 3.3.5 Estimated prostate gland > 100 grams (within 8 weeks prior to study enrollment)
- 3.3.6 Previous radical surgery (prostatectomy) or cryosurgery for prostate cancer
- 3.3.7 Previous pelvic irradiation, prostate brachytherapy, or bilateral orchiectomy
- 3.3.8 Previous hormonal therapy, such as LHRH agonists (e.g. goserelin, leuprolide), anti-androgens (e.g., flutamide, bicalutamide), estrogens (e.g., DES), or surgical castration (bilateral orchiectomy) or planned concurrent androgen deprivation therapy
- 3.3.9 Previous or concurrent cytotoxic chemotherapy for prostate cancer
- 3.3.10 Prosthetic implants in the pelvic region that contain metal or conductive materials (e.g., an artificial hip).
- 3.3.11 Severe, active comorbidity, defined as follows:
  - Unstable angina and/or congestive heart failure requiring hospitalization within the last 6 months
  - Transmural myocardial infarction within the last 6 months
  - Acute bacterial or fungal infection requiring intravenous antibiotics at the time of registration
  - Crohn's Disease or ulcerative colitis
  - Chronic obstructive pulmonary disease exacerbation or other respiratory illness requiring hospitalization or precluding study therapy at the time of registration
  - Hepatic insufficiency resulting in clinical jaundice and/or coagulation defects; note, however, that laboratory tests for liver function and coagulation parameters are not required for entry into this protocol. (Patients on Coumadin or other blood thinning agents are eligible for this study.)
  - Acquired immune deficiency syndrome (AIDS) based upon current CDC definition; note, however, that HIV testing is not required for entry into this protocol. The need to exclude patients with AIDS from this protocol is necessary because the treatments involved in this protocol may be significantly immunosuppressive. Protocol-specific requirements may also exclude immunocompromised patients.

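### Disease-free survival has no rule for men who start non-protocol prostate-cancer therapy before a listed event, so this secondary endpoint is biased upward

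*Combined protocol and SAP*

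**What the plan says.** DFS is defined twice, with the same four events. Section 7.2.1 has: "Disease-free failure events include local progression, distant progression, biochemical recurrence as defined by the RTOG Phoenix definition, and death from any cause". Section 2.2.1 has: "Disease-free failure events include local progression, distant progression, biochemical failure as defined by the RTOG Phoenix definition, and death from any cause". Neither mentions the start of further cancer treatment, and neither gives a censoring rule.

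Hormonal treatment is dealt with only at entry. The schema requires "No prior or planned androgen deprivation or bilateral orchiectomy", and exclusion 3.3.8 rules out previous hormonal therapy "or planned concurrent androgen deprivation therapy". Nothing is said about therapy begun after SBRT.

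On follow-up, section 2.3 says "Followup will continue for each enrollee up to three years after enrollment", and section 6.5 says "PSA will be assessed before or at each follow-up visit". Section 6.5 also lets visits take place with referring providers. The only censoring rule in the plan is in section 7.1, and it applies to the time to late adverse events.

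**The concern.** A time-to-failure endpoint needs a rule for men who are treated for suspected failure before failure is documented. Here that rule matters because PSA is the main scheduled means of detecting relapse. After treatment, the table in section 6.6 lists no imaging or biopsy, and section 6.5 leaves the digital rectal examination to the physician's discretion.

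Suppose a man's PSA rises and he starts androgen deprivation before he meets the biochemical definition. His PSA then falls, and nothing else on the schedule is likely to register a failure within three years. The treatment given because relapse was suspected removes the evidence of relapse from the endpoint. At stake is whether the reported DFS overstates disease control. DFS is the trial's only listed efficacy endpoint, and section 1.1 sets out to shorten treatment without losing efficacy.

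**Working it through.** **The plan's own figures.** The plan states no DFS rate, target, event count, test or power, so there is no DFS figure to reproduce. The only power figures stated for ruling out a rate with 60 men are for grade 3 or higher rectal toxicity (section 7.1), and they do reproduce:

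- True rate 1.5%: P(X ≤ 1) = 0.985^60 + 60 × 0.015 × 0.985^59 = 0.773, against the stated 77%. The one-sided 95% Wilson upper limit for 1/60 is 7.1%, as stated.
- True rate 2.5%: P(X ≤ 2) = 0.8105, against the stated 81%. The same limit for 2/60 is 9.6%, as stated.

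Neither figure uses DFS. The stopping rule in 7.4 does not use it either, since it counts grade 3+ GU and GI events.

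**Inputs for DFS.**

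- n = 60, single arm (sections 2.3 and 7.3).
- Four listed events (sections 2.2.1 and 7.2.1).
- e = men with a listed event. Not given; 3 and 6 are assumed below.
- s = men who start non-protocol therapy first and never reach a listed event. Not given; 1, 3 and 6 are assumed below.

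**Where such a man goes under the current text.** There are three possibilities.

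1. He is left in follow-up as event-free.
2. The analyst censors him when the therapy starts.
3. He later meets a listed event. He then counts as a failure, but later than the relapse that prompted treatment.

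Only the third records a failure, and it is the one that a lowered PSA makes less likely.

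**Size if left event-free.** With complete follow-up, DFS as written is 1 − e/60. DFS with the start of therapy counted is 1 − (e + s)/60. The difference is s/60, so one man is 1/60 = 1.7 points.

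| Listed events e (assumed) | DFS as written | s = 1 | s = 3 | s = 6 |
|---|---|---|---|---|
| 3 | 95.0% | 93.3% | 90.0% | 85.0% |
| 6 | 90.0% | 88.3% | 85.0% | 80.0% |

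**Size if censored.** Take e = 3 and s = 1, with all others followed to the end.

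- If the three listed events come after the censoring, the Kaplan-Meier estimate is 1 − 3/59 = 56/59 = 94.9%.
- If they come before it, the estimate is 57/60 = 95.0%.
- With the start of therapy counted as an event, DFS is 56/60 = 93.3%.

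The gain is therefore 1.6 to 1.7 points. Censoring assumes that he has the same outlook as the men still at risk. That is doubtful for a man treated because his PSA was rising, so the censoring is informative and the bias has the same direction.

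**Against the precision available.** With 3 events in 60 the exact 95% interval for DFS is 86.1% to 99.0%. One man's 1.7 points lie well inside it.

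**The case against.** Several points on the other side are fair.

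- **The event list may be open.** It is introduced by a word that can be read as non-exhaustive. But no further event is given anywhere, so an open list leaves the choice to the analyst after the data are seen.
- **The biochemical definition is cited, not reproduced.** The documents do not show whether it deals with therapy started before the PSA threshold is met. That limits certainty, and writing the rule down settles it.
- **Handling is unspecified rather than wrong.** A reader might infer that such a man is certain to be counted disease-free to 36 months. The documents do not say so, since DFS has no censoring rule and he could be censored. What stands is that neither course counts him as a failure.
- **Some salvage is already covered.** Local treatment for established local relapse follows a listed event. The gap is mainly androgen deprivation, or other therapy begun without documented progression.

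Three stronger readings are tempting and should be left aside.

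- A reader might convert the 90% five-year freedom from biochemical recurrence in section 1.3 to a constant hazard: −ln(0.90)/5 = 0.0211 per year. That gives 60 × (1 − exp(−0.0632)) = 3.7 failures by three years, from which one might infer that one or two treated men erase 27% to 54% of them. That only restates the assumed one or two men. The source was also a 40-man cohort of lower risk, treated to a different dose.
- A reader might infer that one or two men would change the trial's answer. DFS has no target or test whose answer could change.
- A reader might infer that toxicity of later therapy is wrongly charged to SBRT, because section 7.1 follows each man "to the time of the worst late adverse event". But section 5.9 provides for attribution of adverse events to study therapy, and counting all late events is conservative for safety. Truncating toxicity or quality of life when such therapy starts would be a preference, not a correction.

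The lack of a visible data field for later therapy is weak evidence. The follow-up form in Appendix 3 breaks off as shown, section 6.5 requires an interval history, and section 6.7 allows other pertinent data.

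**Conclusion.** The gap is real and has a known direction. Both definitions of DFS omit the start of non-protocol prostate-cancer therapy, and nothing elsewhere supplies an event, a censoring rule or a rule for PSA measured on hormonal treatment. DFS is overstated by up to 1.7 points for each man affected.

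This rests on three assumptions:

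- The therapy is started because relapse is suspected.
- He does not go on to meet a listed event by the time point.
- All 60 men are otherwise followed to that time point. With fewer men at risk, each step in a Kaplan-Meier curve would be larger.

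The documents give no rate for early salvage, so the total bias cannot be estimated. The consequence is confined to a secondary, descriptive endpoint. Sample size, power, the stopping rule and the primary toxicity conclusion are unaffected. The change is worth making because the event list, followed as written, favours the treatment and is cheap to repair.

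**What to change.** - In 2.2.1 and 7.2.1, add as a DFS event: *start of any non-protocol prostate-cancer therapy, dated at its start, if earlier than the other events*.
- Report a sensitivity analysis that censors at that date instead.
- Confirm that the type and start date of such therapy are recorded at follow-up, including for men seen by referring providers.

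The cost is a clause in two definitions, one extra analysis of a secondary endpoint and, if not already collected, one follow-up item. Treatment and visits do not change. The downside is that DFS may come out slightly lower and will depend partly on discretionary treatment decisions. The censoring analysis shows how much the result depends on that choice.
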